8.3.7 Meal test

UTN: U1111-1118-2480

EudraCT no.: 2010-024054-11

The Subject will undergo a standardised liquid meal test at certain visits (see section 2) and will have their 30 minute and 1 to 4 hour PPG measured. During that time 6 blood samples will be drawn, as specified in the Table 8–2. The samples will be analysed by the central laboratory and the values transferred directly into the trial database.

The Subject must attend the meal test visits in a fasting condition, as detailed in section 8.1.7. Bolus infusion and other medication which should be taken before, in a relation to or after a meal should be withheld until the meal test has been performed.

The Subject should before the meal test be instructed to:

- Follow normal routine regarding eating and exercise habits on the day prior to the meal test
- Refrain from intake of alcohol and use of medications that affect motility (i.e. prokinetics, anticholinergics, tricyclic antidepressants) on the day prior to the meal test, unless the Subject was on this medication at trial entry and does not change the product or product dose
- Not to make any changes in the current basal rate setting 4 hours prior to the meal test
- Measure a SMPG value at 4 AM the night before and in the morning before the meal test. The 4 AM SMPG value and before-meal-test SMPG value is part of the 9-point profile
- Change infusion set and reservoir in the morning the day before the meal test
- Continue to wear the CGM device until end of meal test
- Take a correction bolus according to guidance from Bolus Wizard® if the PG value above the target level

There should be a minimum of four hours between any correction bolus dose and the start of the meal test.

Protocol	1	Date:	04 February 2016	Novo Nordisk
Trial ID: NN1218-3854		Version:	4.0	

 Trial ID: NN1218-3854
 Version:
 4.0

 UTN: U1111-1118-2480
 Status:
 Final

 EudraCT no.: 2010-024054-11
 Page:
 67 of 149

Any hypoglycaemic episodes from midnight before the meal test should be treated and the hypoglycaemic episode should be recorded in the diary, please see section 8.3.3.1. In this case, the meal test should be re-scheduled within the visit window and at Visit 6 before randomisation to trial product.

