The meal test must not be scheduled on the first or seventh day after having fitted the second sensor. Hence the fitting of the sensors must be scheduled accordingly and as a minimum one day before the meal test visit; please see Table 8–3. The rationale for this is: firstly, the sensor will not start measuring IG until after the 2-hour start-up calibration on the first day, and the Subject will have to wait two hours after the sensor insertion before the meal test can start. Secondly, the risk of the CGM device stopping before or during the meal test is possible as the CGM device will automatically stop recording data exactly seven days after sensor insertion.

Table 8–3 Overview of scheduled CGM sensor fitting and removal days relative to meal test based on two sensor periods

Visit		,	V4/V12	/V20 (±	-3 days))		P5/P13/P21 (±3 days)				V 6/ V22(A*)						
Days	-17	-16	-15	-14	-13	-12	-11	-10	-9	-8	-7	-6	-5	-4	-3	-2	-1	0
Procedure					Sched	lule Fitt	ing 1		Schedule Removal 1 and Fitting 2			Meal test and Removal 2						

^{*}Fitting and removal need to be scheduled as soon as the Investigator becomes aware of premature discontinuation of trial product of a Subject.

During the fitting visit, the Investigator will insert a glucose sensor under the Subject's skin, measuring the concentration of glucose in the interstitial fluid every five minutes. The sensor is attached to a transmitter and both are worn by the Subject. The transmitter will transfer the IG data automatically to the receiver where data is stored.

Removal of the first sensor and fitting of the second sensor can be performed at home by the Subject if the Subject has been trained and is able to perform it correctly; according to the Investigator judgment.

In order to ensure that the CGM device is measuring correctly the abdominal insulin infusions site must be in a distance of minimum 7.6 cm (three inches) from where the CGM sensor has been inserted. This will also ensure that local skin reactions, if any, may be related to the correct trial product and/or device.

The Subject should be instructed to remove the CGM device prior to any x-ray, computerised tomography (CT) scan or magnetic resonance imaging (MRI).

Protocol		Date:	04 February 2016	Novo Nordisk
Trial ID: NN1218-3854	CONFIDENTIAL	Version:	4.0	
UTN: U1111-1118-2480	CONFIDENTIAL	Status:	Final	

76 of 149

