- Incidence of episodes with IG ≤2.5, 3.0, 3.5, 3.9 mmol/L [45, 54, 63, 70 mg/dL]) and IG >10.0, 12.0 mmol/L [180, 216 mg/dL])
- Percentage of time spent within IG target range 4.0-10.0mmol/L (71-180 mg/dL)
- Change from baseline in mean of the IG profile

The mean of the IG profile will be defined as:

$$\overline{IG} = \frac{1}{T} \int_{0}^{T} IG(t) dt$$

where T is the time length of the profile and IG(t) is the IG value at time t. (Here t=0 represents the time point for the start of the profile.) This mean will be calculated by means of the linear trapezoidal technique.

• Variation in the IG profile

The variation in the IG profile will be defined as:

$$\frac{1}{T} \int_{0}^{T} \left| IG(t) - \overline{IG} \right| dt$$

where T is the time length of the profile, IG(t) is the IG value at time t, and \overline{IG} is the mean of the IG profile as defined above. (Again, here t=0 represents the time point for the start of the profile.) The integral will be calculated by the linear trapezoidal technique. The coefficient of variation (CV%) will also be calculated to describe the IG variation.

• Change from baseline in the AUC_(3.9-IG) for IG \leq 3.9 mmol/L [70 mg/dL]

 Trial ID: NN1218-3854
 CONFIDENTIAL
 Version: Status: Final Page: 122 of 149

 EudraCT no.: 2010-024054-11
 Page: 122 of 149

The AUC _(3.9-IG) is defined for each Subject at each CGM period as the AUC _(3.9-IG) when IG is below or equal to 3.9 mmol/L [70 mg/dL] from the first valid sensor value divided by the actual duration of the profile. The AUC will be calculated by the linear trapezoidal technique. If the profile has missing censor values, then the AUC should be calculated for each profile part consisting of non-missing censor values. The endpoint is then calculated as the sum of the AUCs for all profile parts divided by the sum of the duration of the profile parts for which AUC is calculated.

IG measurements during meal test will be excluded.

All CGM endpoints will be summarised descriptively by treatment.

Supportive secondary CGM and meal-characteristics endpoints

The following endpoints will be assessed 16 weeks after randomisation:

• Change from baseline in mean IG increment (0-30 min, 0-1 hour and 0-2 hours after start of the meal)

The mean IG (meal) increment will be defined as the mean across main meals of the prandial increments, i.e. the difference between IG 30 (1 or 2 hours, respectively) after the meal and IG before the meal

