1.2 Scope of the statistical analysis plan

This statistical analysis plan (SAP) is based on the statistical considerations of NN1218-3854 as planned in the trial protocol *Efficacy and Safety of Continuous Subcutaneous Insulin Infusion of Faster-acting Insulin Aspart compared to NovoRapid[®] in Adults with Type 1 Diabetes*, version 4.0 (dated 04 February 2016). It contains a more detailed description for deriving and calculation of endpoints. Furthermore, it details changes to the statistical considerations presented in the protocol.

The changes to the statistical considerations proposed in this SAP and the reasons for the changes will be reported in the clinical trial report (CTR).

2 Statistical considerations

General considerations

In general, for endpoints evaluated as a change from baseline and/or where a baseline adjustment is made, baseline is defined as information collected at randomisation (Visit 6). In case a measurement is not available at randomisation, the most recent measurement prior to randomisation will be used as baseline.

Two observation periods are defined, “in-trial” and “on-treatment”, and it will be specified which period each analysis will use.

- **In-trial:** the observation period from date of randomisation and until last trial -related Subject-site contact. The in-trial observation period includes data collected after discontinuation of randomised treatment.
- **On-treatment:** the observation period from date of first dose of randomised NovoRapid[®]/fast-acting insulin aspart and no later than 7 days after the day of last dose of randomised NovoRapid[®]/fast-acting insulin aspart. The on-treatment observation period includes data collected up to and including 7 days after discontinuation of randomised treatment.

All efficacy endpoints will be summarised and analysed using the full analysis set (FAS), unless otherwise stated. Safety endpoints will be summarised using the safety analysis set and analysed using the FAS.

Presentation of results from a statistical analysis will include the estimated mean treatment effects (LSMeans) for change from baseline, if applicable. Estimated mean treatment differences (or ratios) will be presented together with two-sided 95% confidence interval (CI) for all endpoints analysed statistically.

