Step 4 in the hierarchical testing procedure is to confirm superiority of change from baseline in 1,5-anhydroglucitol 16 weeks after randomisation with fast-acting insulin aspart compared to NovoRapid[®].

The change from baseline in 1,5-anhydroglucitol will be analysed using a model similar to 1), but with baseline 1,5-anhydroglucitol as a covariate.

Superiority will be confirmed if the upper boundary of the two-sided 95% confidence interval of the mean treatment difference (fast-acting insulin aspart minus NovoRapid[®]) is below 0.

Change from baseline of time spent in low IG (≤ 3.9 mmol/L [70 mg/dL]) during CGM 16 weeks after randomisation (Step 5)

The time spent in low IG is defined for each Subject at each CGM period as the accumulated time in hours spent below or equal to 3.9 mmol/L [70 mg/dL] from the first valid sensor value divided by the actual duration of the profile. To report the endpoint in minutes per 24 hours the ratio is multiplied by 1440.

Step 5 of the hierarchical testing procedure is to confirm superiority of change from baseline of time spent in low IG (≤ 3.9 mmol/L [70 mg/dL]) during CGM 16 weeks after randomisation with fast-acting insulin aspart compared to NovoRapid[®].

The change from baseline of time spent in low IG (≤ 3.9 mmol/L [70 mg/dL]) will be analysed with a model similar to 1), but with the corresponding baseline value as covariate.

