where T is the time length of the profile, $IG(t)$ is the IG value at time t , and \overline{IG} is the mean of the IG profile as defined above. (Again, here $t=0$ represents the time point for the start of the profile.) The integral will be calculated by the linear trapezoidal technique. The coefficient of variation (CV%) will also be calculated to describe the IG variation.

- Change from baseline in the area under the curve (AUC)_(3.9-IG) for IG \leq 3.9 mmol/L [70 mg/dL]

The AUC_(3.9-IG) is defined for each Subject at each CGM period as the AUC_(3.9-IG) when IG is below or equal to 3.9 mmol/L [70 mg/dL] from the first valid sensor value divided by the actual duration of the profile. The AUC will be calculated by the linear trapezoidal technique. If the profile has missing sensor values, then the AUC should be calculated for each profile part consisting of non-missing sensor values. The endpoint is then calculated as the sum of the AUCs for all profile parts divided by the sum of the duration of the profile parts for which AUC is calculated.

IG measurements during meal test will be excluded.

All CGM endpoints will be summarised descriptively by treatment.

Supportive secondary CGM and meal-characteristics endpoints

The following endpoints will be assessed 16 weeks after randomisation:

- Change from baseline in mean IG increment (0-30 min, 0-1 hour and 0-2 hours after start of the meal)

The mean IG (meal) increment will be defined as the mean across main meals of the prandial increments, i.e. the difference between IG 30 min (1 or 2 hours, respectively) after the meal and IG before the meal

- Change from baseline in mean IG peak after start of meal

The mean IG peak after start of meal will be derived as mean across main meals of the IG maximum values within 4 hours after start of the meal.

- Change from baseline in mean time to the IG peak after meal

The mean time to the IG peak after meal is derived as the mean time to the IG peak across main meals.

These endpoints will also be derived for each main meal separately (breakfast, lunch and main evening meal). IG measurements during meal test will be excluded. All endpoints will be analysed separately, using a model similar to 1) except with the corresponding baseline value as covariate.

All CGM endpoints will be summarised descriptively by treatment.

Supportive secondary efficacy endpoints related to CGM and meal test

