In the statistical analysis for subjects reaching HbA_{1c} or PPG (SMPG) targets it has been clarified that subjects without an HbA_{1c} measurement or 1-hour mean PPG measurement at week 16 will be handled as non-responders in the on-treatment observation period analysis.

Change from baseline has been removed for fluctuation in the 7-7-9-point SMPG profile as it is analysed logarithmically transformed and change from baseline values could be negative.

CGM endpoints

Percentage of time spent with IG ≤ 3.9 mmol/L [70 mg/dL] has been added to align with the thresholds for IG for the endpoints incidence of episodes.

The percentage of time spent with IG > 13.9 mmol/L [250 mg/dL] and incidence of episodes with IG > 13.9 mmol/L [250 mg/dL] has been added to further evaluate the effect and safety of fast-acting insulin aspart.

It has been clarified the variation in the IG profile will be presented by the fluctuation.

The change from baseline in $\Delta\text{AUC}_{\text{IG},0-15\text{min}}$, $\Delta\text{AUC}_{\text{IG},0-30\text{min}}$, $\Delta\text{AUC}_{\text{IG},0-1\text{h}}$, $\Delta\text{AUC}_{\text{IG},0-2\text{h}}$ and $\Delta\text{AUC}_{\text{IG},0-4\text{h}}$ are added to further evaluate the effect and safety of fast-acting insulin aspart.

It has been clarified that the endpoints related to CGM and meal test derived as AUCs will be weighted by the duration.

Adverse events

For adverse events summaries by relation to device has been change to relation to technical complaint to align with what is reported on the case report forms. Summaries for AEs leading to withdrawal from trial have been added to further investigate the safety of fast -acting insulin aspart.

Hypoglycaemic episodes

The endpoints treatment emergent hypoglycaemic episodes occurring within 1 (exclusive) to 2 hours (inclusive), 2 (exclusive) to 3 hours (inclusive), 3 (exclusive) to 4 hours (inclusive) after start of the meal has been added to further investigate the safety of fast-acting insulin aspart.

It has been clarified that separate statistical analysis will only be for all severe hypoglycaemic episodes as the number is expected to be very low.

Unexplained hyperglycaemic episodes

The treatment emergent definition for unexplained hyperglycaemic episodes has been clarified.

Assessments not collected at baseline

ECG and fundus photography/fundoscopy is not collected at baseline, hence change from screening will be summarised for these endpoints instead.

4 References

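### Is the confirmatory time-in-low-glucose endpoint (Step 5) left undefined for missing sensor time and for meal-test readings?

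*SAP*

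**What the plan says.** **Step 5.** For each CGM period, time at or below 3.9 mmol/L is accumulated from the first valid sensor value and "divided by the actual duration of the profile. To report the endpoint in minutes per 24 hours the ratio is multiplied by 1440" (SAP 2.4.1 and protocol 17.4.1). Neither text adds a rule for gaps or for the meal test.

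**Supportive AUC(3.9−IG).** This starts with the same denominator and then adds a gap rule. In protocol 17.4.2.1, if values are missing, "then the AUC should be calculated for each profile part consisting of non-missing censor values" (the SAP corrects the misspelt word). The total is "divided by the sum of the duration of the profile parts for which AUC is calculated" (SAP 2.4.2.1). The rule is written for this endpoint only; the percentage-of-time endpoints beside it have none.

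**Meal test.** The supportive CGM group closes with "IG measurements during meal test will be excluded" (SAP 2.4.2.1; also protocol 17.4.2.1). The subject's instruction is "Continue to wear the CGM device until end of meal test" (protocol 8.3.7), so the test lies inside the Visit 6 and Visit 22 profiles.

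**Sensors.** Each period of 11 to 13 days needs a second sensor, and "the sensor will not start measuring IG until after the 2-hour start-up calibration on the first day" (protocol 8.5.1.3).

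**SAP scope and changes.** SAP 1.2 says of the SAP: "It contains a more detailed description for deriving and calculation of endpoints". SAP section 3 clarifies only the baseline covariate for Step 5. It also notes that percentage of time at or below 3.9 mmol/L "has been added to align with the thresholds for IG for the endpoints incidence of episodes".

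**Target range.** Protocol 4.2.3.3 lists time in range as 4.0–7.8 mmol/L. Protocol 17.4.2.1 and SAP 2.4.2.1 give 4.0–10.0 mmol/L.

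**The concern.** A confirmatory endpoint should have one derivation. As written, the denominator could be elapsed time or recorded time. A supportive endpoint that uses the same words was given an explicit rule, and the confirmatory one was not. Gaps are certain, because every profile spans two sensors.

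The meal test raises a similar question. It uses a standardised meal and a weight-based bolus. At Visit 22 it is done on randomised product, so counting it could in principle act differently in the two arms. The SAP now also reports percentage of time at or below 3.9 mmol/L in a group that excludes the test. The trial report could therefore show two slightly different figures for closely related quantities (1% of 1440 min = 14.4 min/24 h).

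At stake would be the Step 5 estimate and, if gaps or low readings in the test differed by arm, the Step 5 comparison.

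**Working it through.** The sample-size section covers Steps 1 and 2 only. The plan states no mean, SD, expected data capture or power for Step 5, so there is no figure of its own to reproduce. The check is on the definition.

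**Inputs.** Period 11–13 days = 264–312 h (protocol 8.5.1). Second-sensor start-up 2 h (8.5.1.3). Last meal-test sample at 4 h (8.3.7). Time in low IG is not given, so 30–120 min/24 h is assumed.

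**1. Denominator.** If a share g of the profile is missing, the elapsed-time value equals the recorded-time value × (1 − g).
- Start-up gap: 2/312 = 0.64% to 2/264 = 0.76%. Leaving out the first sensor's own 2 h start-up gives 2/310 = 0.65% to 2/262 = 0.76%.
- Understatement under the elapsed reading: 30 × 0.0064 = 0.2 to 120 × 0.0076 = 0.9 min/24 h.
- With the same g in both arms and both periods, the treatment difference and the SD are both multiplied by (1 − g). Their ratio, and so the test, does not change.

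The elapsed reading is also the less natural one. It would count unobserved time as time not low. Step 5 starts the clock at the first valid sensor value, which already drops unrecorded time at the front of the profile.

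**2. Meal test.** Let r be the rate outside the test (min/24 h), L the low minutes in the test and D the period in days. If the test is excluded, the value is r. If it is included, both the numerator and the 4 h of denominator enter:

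shift = (L − r × 4/24) / D

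| r assumed | expected in 4 h | shift if L = 0 | shift if L = 10 |
|---|---|---|---|
| 30 | 5 min | −0.38 to −0.45 | +0.38 to +0.45 |
| 60 | 10 min | −0.77 to −0.91 | 0 |
| 120 | 20 min | −1.54 to −1.82 | −0.77 to −0.91 |

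The test is 4/312 = 1.3% to 4/264 = 1.5% of the period. A 10-minute difference between arms in low time during the Visit 22 test, with equal rates outside it, would move the treatment difference by 10/13 = 0.77 to 10/11 = 0.91 min/24 h. Long low spells are unlikely. Under protocol 8.3.7 the test starts at 4.0–8.8 mmol/L, is followed by 78 g of carbohydrate, and self-measured values at or below 3.9 mmol/L are treated.

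**3. Which readings belong to Step 5.** Protocol 4.2.2 lists the endpoint as measured during CGM, without qualification. The headings of 4.2.3.2 and 4.2.3.3 carry the meal-test exclusion in their titles, and 4.2.3.4 holds the meal-test CGM endpoints. The exclusion is thus a label on supportive groups, and Step 5 uses the whole period.

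**4. Target range.** Protocol 4.2.3 says its entries are a bare list and sends the reader to 17.4.2 for detail. Protocol 17.4.2.1 and the SAP agree on 4.0–10.0 mmol/L.

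**The case for a change.** The strongest reply is that a confirmatory derivation should not depend on inference. The AUC endpoint has the same wording and its authors still thought a gap rule was needed. Unscheduled signal loss could also exceed 2 h by a wide margin. At an assumed 5–20% loss and 60–120 min/24 h, the elapsed reading would lower values by 3–24 min/24 h. With 5% loss in one arm and 10% in the other, it would create a spurious difference of 3–6 min/24 h.

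It stands that the text is silent on both points, and that one sentence would have settled each. The rest is weaker. The AUC has its own reason for a rule: the trapezoidal method would otherwise interpolate across gaps. The rule can also be read as the documents' own explanation of the shared phrase. The 5–20% figures are not in the documents, and the harm needs both the less natural denominator and unequal capture. The trial is double-blind with visually identical products, all subjects are issued a blinded study CGM device, low capture leads to re-training, and lost sensors can be replaced (protocol 8.5.1.3, 8.5.1.6). Nothing suggests that capture would differ by arm. Programming and data review use a fake randomisation (SAP 2.2), which limits the scope for a choice driven by results.

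The overlap with the supportive endpoint is real but loose. Step 5 is a tested change from baseline; the other is a percentage at week 16, summarised descriptively.

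**Conclusion.** The silence is real, but it is a gap in detail that an analyst fills sensibly: recorded time in the denominator, and the whole CGM period for Step 5. On that reading the endpoint is sound. The alternatives differ by under 1% of the value for the only gap of stated length. For the meal test they differ by about −1.8 to +0.5 min/24 h with 0 to 10 low minutes. Step 5 is last in the hierarchy and is tested only if Steps 1–4 succeed. The target-range mismatch is a listing slip in a descriptive endpoint and touches neither alpha nor power.

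This rests on 30–120 min/24 h as the time in low IG, which the documents do not give, and on data capture being similar in the two arms. No change to the plan is needed.

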2.4.2 Supportive secondary endpoints

2.4.2.1 Efficacy endpoints

All endpoints except insulin dose and insulin pump parameters in this section will be assessed using the FAS and the in-trial observation period and repeated using the on-treatment observation period. Insulin dose and insulin pump parameters will be presented using the safety analysis set and will therefore only use the on-treatment observation period.

Change from baseline in FPG to 16 weeks after randomisation

Change from baseline in FPG 16 weeks after randomisation will be analysed on all planned post-baseline measurements until or at 16 weeks with a model similar to 1) except with baseline FPG as covariate.

Percentage of Subjects reaching HbA_{1c} target 16 weeks after randomisation:

HbA_{1c} < 7.0%

A dichotomous (responder/non-responder) endpoint will be defined based on whether a Subject has met the HbA_{1c} target (HbA_{1c} <7.0% (53 mmol/mol)) 16 weeks after randomisation.

This responder endpoint will be analysed based on a logistic regression model using treatment, strata (two levels based on use of own CGM or not), previous insulin use (three levels: NovoRapid[®], Apidra[®], Humalog[®]), and region as factors, and baseline HbA_{1c} as covariate. In analysis of the in-trial observation period Subjects without an HbA_{1c} measurement at week 16 will be treated as non-responders. In the on-treatment observation period analysis Subjects who discontinue fast-acting insulin aspart/NovoRapid[®], withdraw from trial, and/or have no HbA_{1c} measurement at week 16 are included as non-responders.

HbA_{1c} <7.0 % without severe hypoglycaemia

A dichotomous (responder/non-responder) endpoint will be defined based on whether a Subject has met the HbA_{1c} target (HbA_{1c} <7.0% (53 mmol/mol)) 16 weeks after randomisation without treatment emergent severe hypoglycaemic episodes.

This responder endpoint will be analysed based on a logistic regression model using treatment, strata (two levels based on use of own CGM or not), previous insulin use (three levels: NovoRapid[®], Apidra[®], Humalog[®]), and region as factors and baseline HbA_{1c} as covariate. In the analysis of the in-trial observation period Subjects without an HbA_{1c} measurement at week 16 will be treated as non-responders. In the on-treatment observation period analysis Subjects who discontinue fast-acting insulin aspart/NovoRapid[®], withdraw from trial, or have no HbA_{1c} measurement at week 16 are included as non-responders.

Change from baseline in 30- min, 1- hour, 2- hour, 3- hour and 4- hour PPG and in 30- min, 2- hour, 3- hour and 4- hour PPG increment after 16 weeks after randomisation (meal test)

Laboratory measured PG from the meal test will be analysed for 30 minutes, 1-hour, 2-hours, 3-hours and 4-hours PPG separately. The corresponding PPG increments will be derived separately using each PPG measurement minus the pre-prandial PG.

Change from baseline in PPG and PPG increment 16 weeks after randomisation will be analysed separately using a model similar to the model used in hierarchical testing procedure step 2 for 1 -

hour PPG increment 16 weeks after randomisation (meal test) except with the corresponding baseline value as covariate.

Change from baseline in endpoints derived from the 7-7-9 point self-measured plasma glucose (SMPG) profile 16 weeks after randomisation

PPG and PPG increments based on the 7-7-9-point SMPG profiles will be derived separately for PG measurements made 1 hour after the meal. In the following section this distinction will be considered implicit and without further explanation.

Pre-prandial PG and PPG will be recorded by the Subjects as part of the 7-7-9 point SMPG profile prior to three defined visits. Individual mean mealtime PPG (post-breakfast, post-lunch, post-main evening meal) will be derived from the three profiles. Overall mean PPG will be derived from the individual derived mealtime PPG values.

PPG increment for each meal (breakfast, lunch, main evening meal) will be derived from the 7-7-9 point SMPG profile as the difference between PPG values and the PG value before meal in each separate profile. The mean of the derived increments will then be calculated separately for each meal. Mean 1 hour PPG increments over all meals will be derived as the mean of all corresponding mean meal increments.

- Change from baseline in mean of the 7-7-9-point SMPG profile

The mean of the 7-7-9-point SMPG profile is defined as the area under the curve profile divided by the measurement time, and is calculated using the linear trapezoidal technique.

Change from baseline in the mean of the 7-7-9-point SMPG profile 16 weeks after randomisation will be analysed using a model similar to 1) except with the corresponding baseline value as covariate.

- Change from baseline in mean pre-prandial PG, PPG and PPG increment over all three meals

Change from baseline in mean pre-prandial PG, PPG and PPG increment 16 weeks after randomisation will be analysed separately using a model similar to 1), except with the corresponding baseline value as covariate.

- Change from baseline in individual meal (breakfast, lunch and main evening meal) PPG, PPG increment and pre-prandial PG (pre-breakfast, pre-lunch, pre-main evening meal)

Change from baseline in PPG, PPG increment and pre-prandial PG endpoints 16 weeks after randomisation for the individual meals will be analysed separately using a model similar to 1) except with the corresponding baseline value as covariate.

- Fluctuation in 7-7-9-point profile

The fluctuation in the 7-7-9-point profile is defined as:

$$\frac{1}{T} \int_0^T |PG(t) - \overline{PG}| dt,$$

where T , $PG(t)$ and \overline{PG} denotes the length of the profile, the PG value at time t and the mean of the profile, respectively.

Fluctuation in the 7-7-9-point profile will be logarithmically transformed and analysed in the same way as mean of the profile is analysed except with the corresponding log-transformed baseline value as covariate.

Estimated treatment means and the estimated treatment difference with corresponding 95% CI will be back-transformed to the original scale, resulting in estimated geometric means, a treatment ratio and a 95% CI for the treatment ratio.

- Change in nocturnal SMPG measurements

Change from baseline in nocturnal SMPG measurements will be assessed by considering the differences between PG values available at bedtime, at 4 AM and the before breakfast value the following day: (4 AM PG value minus at bedtime PG value), (before breakfast PG value minus at bedtime PG value) and (before breakfast PG value minus 4 AM PG value).

Change from baseline in nocturnal SMPG measurements 16 weeks after randomisation will be analysed in the same way as mean of the profile is analysed, except with the corresponding baseline values as covariate. .

Percentage of subjects reaching PPG target (based on mean of PPG measurements in SMPG) 16 weeks after randomisation:

- Overall PPG (1 hour) ≤ 7.8 mmol/L [140 mg/dL]

A dichotomous (responder / non-responder) endpoint will be defined based on whether a Subject has reached an overall mean 1 hour PPG ≤ 7.8 mmol/L [140 mg/dL] 16 weeks after randomisation, where PPG is derived from the 7-7-9 point SMPG profile.

This responder endpoint will be analysed based on a logistic regression model using treatment, strata (two levels based on use of own CGM or not), previous insulin use (three levels: NovoRapid[®], Apidra[®], Humalog[®]), and region as factors, and baseline overall 1-hour mean PPG as covariate. In analysis of the in-trial observation period Subjects without an overall mean 1 hour PPG at week 16 will be treated as non-responder. In the on-treatment observation period analysis Subjects who discontinue fast-acting insulin aspart/NovoRapid[®], withdraw from trial, or have no 1-hour mean PPG measurement at week 16 will be included as non-responders.

- Overall PPG (1-hour) ≤ 7.8 mmol/L [140 mg/dL] without severe hypoglycaemia

A dichotomous (responder / non-responder) endpoint will be defined based on whether a Subject has reached an overall 1-hour PPG ≤ 7.8 mmol/L [140 mg/dL] 16 weeks after randomisation without any treatment emergent severe hypoglycaemic episodes.

This responder endpoint will be analysed based on a logistic regression model using treatment, strata (two levels based on use of own CGM or not), previous insulin use (three levels: NovoRapid[®], Apidra[®], Humalog[®]) and region as factors, and baseline mean 1-hour PPG as covariate. In analysis of the in-trial observation period Subjects without an overall mean 1 hour PPG at week 16 will be treated as non-responders. In the on-treatment observation period analysis Subjects who discontinue fast-acting insulin aspart/NovoRapid[®], withdraw from trial, or have no 1-hour PPG measurement at week 16 will be included as non-responders.

Change from baseline in lipids-lipoproteins profile 16 weeks after randomisation

Change from baseline in lipid endpoints (low density lipoprotein (LDL), high density lipoprotein (HDL), and total cholesterol) will be analysed separately using a model similar to 1). The lipid endpoints will be log-transformed before they are analysed including the corresponding baseline measurement which is included in the analysis as a covariate. The treatment difference and associated 95% confidence intervals will be back-transformed providing results in terms of ratios of geometric means on the original scale.

Insulin dose (Units/day and Units/kg/day; total basal, total bolus, total daily insulin dose and individual meal insulin dose)

The insulin doses will be summarised descriptively by treatment week according to regimen, both by meal type and as total daily dose in units and units/kg (total daily and separately for each meal time dose). The total daily basal dose will be derived from the total daily dose and bolus doses including correction doses. Insulin doses will be summarised using the on-treatment observation period and using the safety analysis set.

Insulin delivery pump parameters

The insulin pump parameters including insulin carbohydrate ratio, glucose sensitivity factor and active insulin time will be summarised descriptively by treatment week. They will be summarised using the on-treatment observation period and using the safety analysis set.

Supportive secondary CGM-related endpoints

All following endpoints will be assessed 16 weeks after randomisation:

- Percentage of time spent with IG $\leq 2.5, 3.0, 3.5, 3.9$ mmol/L [45, 54, 63, 70 mg/dL] and IG $> 10.0, 12.0, 13.9$ mmol/L [180, 216, 250 mg/dL]
- Incidence of episodes with IG $\leq 2.5, 3.0, 3.5, 3.9$ mmol/L [45, 54, 63, 70 mg/dL] and IG $> 10.0, 12.0, 13.9$ mmol/L [180, 216, 250 mg/dL]
- Percentage of time spent within IG target range 4.0-10.0mmol/L (71-180 mg/dL)
- Change from baseline in mean of the IG profile

The mean of the IG profile will be defined as:

$$\overline{IG} = \frac{1}{T} \int_0^T IG(t) dt,$$

where T is the time length of the profile and $IG(t)$ is the IG value at time t . (Here $t=0$ represents the time point for the start of the profile.) This mean will be calculated by means of the linear trapezoidal technique.

- Variation in the IG profile

The variation in the IG profile will be presented by the fluctuation, which is defined as:

$$\frac{1}{T} \int_0^T |IG(t) - \overline{IG}| dt,$$

where T is the time length of the profile, $IG(t)$ is the IG value at time t , and \overline{IG} is the mean of the IG profile as defined above. (Again, here $t=0$ represents the time point for the start of the profile.) The integral will be calculated by the linear trapezoidal technique. The coefficient of variation (CV%) will also be calculated to describe the IG variation.

- Change from baseline in the area under the curve (AUC)_(3.9-IG) for IG \leq 3.9 mmol/L [70 mg/dL]

The AUC_(3.9-IG) is defined for each Subject at each CGM period as the AUC_(3.9-IG) when IG is below or equal to 3.9 mmol/L [70 mg/dL] from the first valid sensor value divided by the actual duration of the profile. The AUC will be calculated by the linear trapezoidal technique. If the profile has missing sensor values, then the AUC should be calculated for each profile part consisting of non-missing sensor values. The endpoint is then calculated as the sum of the AUCs for all profile parts divided by the sum of the duration of the profile parts for which AUC is calculated.

IG measurements during meal test will be excluded.

All CGM endpoints will be summarised descriptively by treatment.

Supportive secondary CGM and meal-characteristics endpoints

The following endpoints will be assessed 16 weeks after randomisation:

- Change from baseline in mean IG increment (0-30 min, 0-1 hour and 0-2 hours after start of the meal)

The mean IG (meal) increment will be defined as the mean across main meals of the prandial increments, i.e. the difference between IG 30 min (1 or 2 hours, respectively) after the meal and IG before the meal

- Change from baseline in mean IG peak after start of meal

The mean IG peak after start of meal will be derived as mean across main meals of the IG maximum values within 4 hours after start of the meal.

- Change from baseline in mean time to the IG peak after meal

The mean time to the IG peak after meal is derived as the mean time to the IG peak across main meals.

These endpoints will also be derived for each main meal separately (breakfast, lunch and main evening meal). IG measurements during meal test will be excluded. All endpoints will be analysed separately, using a model similar to 1) except with the corresponding baseline value as covariate.

All CGM endpoints will be summarised descriptively by treatment.

Supportive secondary efficacy endpoints related to CGM and meal test

Endpoints listed below will be assessed during meal test and based on CGM measurements.

The following endpoints will be assessed 16 weeks after randomisation:

- Change from baseline in $AUC_{IG,0-15min}$
- Change from baseline in $AUC_{IG,0-30min}$
- Change from baseline in $AUC_{IG,0-1h}$
- Change from baseline in $AUC_{IG,0-2h}$
- Change from baseline in $AUC_{IG,0-4h}$
- Change from baseline in time to the IG peak after start of meal
- Change from baseline in IG peak after start of meal

$AUC_{IG,0-15 min}$, $AUC_{IG,0-30 min}$, $AUC_{IG,0-1h}$, $AUC_{IG,0-2h}$, and $AUC_{IG,0-4h}$ will be calculated as the AUC IG using the linear trapezoidal technique and weighted by duration. From these endpoints the increments will also be calculated where an average of the IG concentrations immediately before the meal is subtracted from the weighted AUC. Each endpoint and derived increment will be analysed using an analysis of variance model including treatment, previous insulin use (three levels: NovoRapid[®], Apidra[®], Humalog[®]), region and strata as factors, and the corresponding baseline value as covariate.

The IG peak after start of meal will be derived as the IG maximum values within 4 hours after start of the meal-test meal.

Change from baseline in IG peak and time to IG peak 16 weeks after randomisation will be compared separately between treatments using an analysis of variance model including treatment, strata (two levels based on use of own CGM or not), previous insulin use (three levels: NovoRapid[®], Apidra[®], Humalog[®]), and region as factors, and the corresponding baseline value as covariate.

